13.2 General statistical considerations

The Baseline value is defined as the last nonmissing pretreatment measurement.

13.2.1 Data presentation

For safety and efficacy analyses, study participants will be grouped by their Baseline weight strata (10 to <20kg [22 to <44lb], 20 to <40kg [44 to <88lb], and \geq 40kg [\geq 88lb]). Selected analyses will also group study participants by their Baseline age group, concomitant MTX use, and anti-CZP antibody status. Subgroups defined by CZP dosing regimen will also be displayed. Two CZP dosing regimen subgroups will be defined as follows:

- Original CZP dose regimen: includes all study participants in the SS who began treatment in accordance with the original dosing regimen defined for the study (3 loading doses of CZP at Weeks 0, 2, and 4 [minimum=100mg Q2W, maximum=400mg Q2W] followed by a maintenance dose for the duration of the study [minimum=50mg Q2W, maximum=200mg Q2W]). This subgroup includes all study participants who began the

study with this CZP dose regimen and received 1 or more doses of this regimen, regardless of any subsequent switch to the reduced CZP dose regimen.

- **Reduced CZP dose regimen:** includes all study participants in the SS who began treatment in accordance with the reduced dosing regimen defined for the study (3 loading doses of CZP at Weeks 0, 2, and 4 [minimum=50mg Q2W, maximum=200mg Q2W] followed by a maintenance dose for the duration of the study [minimum=50mg Q4W, maximum=100mg Q2W]). This subgroup includes all study participants who began the study with this CZP dose regimen and received 1 or more doses of this regimen, regardless of any subsequent switch to the original CZP dose regimen.

Summary statistics will consist of frequency tables for categorical variables. For continuous variables, descriptive statistics (number of available observations, mean, median, standard deviation, minimum and maximum) will be presented.

For those parameters likely to have a skewed distribution (eg, CRP), geometric means with associated coefficients of variation and/or quartiles may be presented.

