4.1 Primary variables

4.1.1 Pharmacokinetic and immunological variables

Certolizumab pegol plasma concentrations and anti-CZP antibody levels at Week 16 and Week 48 will be assessed and data will be summarized.

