7.2.1 Procedure for dose change (Protocol Amendment 9)

Following Protocol Amendment 9, study participants will only be enrolled on the original CZP dose regimen. With Protocol Amendment 4, the maintenance dose in the study was reduced by 50% for all weight groups (not applicable for study participants enrolled on the reduced CZP dose regimen per Protocol Amendment 5). Participants on the reduced CZP dose regimen can remain on the reduced CZP dose or may be switched to the original CZP dose regimen at the discretion of the Investigator and in consultation with the medical monitor. Additional dose changes are not allowed. The procedure for dose change is as follows:

- The timepoint of the dose change is the next scheduled time of injection after the Informed Consent form related to the dose change was signed. In case the next scheduled injection was planned for home dosing, the study participant will be requested to return to the clinic for an Unscheduled Visit for signing the Informed Consent form related to the dose change, administration of CZP, and to dispense the new supplies. Unused IMP dispensed previously needs to be returned.
In case the study participant is not able to visit the site for that next scheduled injection, then the dose change must be performed at the next scheduled injection.

- Study participants will be monitored at least every 4 weeks over a period of 12 weeks after the dose change, either at the regularly scheduled visits or at additional Unscheduled Visits. The Unscheduled Visits will be scheduled to match with the dosing schedule, ie, the study medication will be administered at the day of the Unscheduled Visit. The Investigator should consult with the Medical Monitor in case of any questions related to the timing of the dose change or the Unscheduled Visits.
 - Study participants undergoing the dose change at an Unscheduled Visit between the regular visits will be required to return at the latest after 4 weeks for an Unscheduled Visit in case no regular visit is scheduled within 4 weeks. These study participants will be monitored at least every 4 weeks over a period of 12 weeks.

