13.4 Planned PK, PD, and immunological variable analysis

Certolizumab pegol plasma concentrations levels at Week 16 and Week 48 will be assessed as primary variables in this study. Other PK and immunological variables include CZP plasma concentrations at other study timepoints and anti-CZP antibody levels throughout the study.

Plasma CZP concentrations will be used to build a PopPK model with the nonlinear mixed-effect modeling (NONMEM) software. The model will be parameterized in terms of clearance, volume of distribution, and absorption rate constant. Details of the PopPK modeling procedures will be described in a separate data analysis plan. The pediatric PopPK model will be combined with PD data (PedACR) and if the data allow, an exposure response relationship will be derived. These modeling analyses and results will be reported separately.

All study participants enrolled following Protocol Amendment 9 will have plasma CZP concentrations and anti-CZP antibodies analyzed using the ECLIA method. In addition, PK and ADA samples (for which sufficient volume is available) collected in this study prior to Protocol Amendment 9 will be analyzed with the ECLIA method.

Data from the ECLIA method will constitute the study's main PK and anti-CZP antibody evaluations. As such, PK and anti-CZP antibody data generated with the original ELISA method will be reported as Listings. Plasma CZP concentration data generated by the ECLIA method will be tabulated and summarized (geometric mean, arithmetic mean, minimum, maximum, standard deviation and % coefficient of variation) by study dose regimen (original CZP dose regimen or reduced CZP dose regimen) for each PK sampling visit. Plasma concentration time curves will be plotted, along with respective individual anti-CZP antibody titers where available, separately for study participants who began treatment according to the original CZP dose regimen or the reduced CZP dose regimen, overall, and by Baseline age stratum. Subgroup analyses will include study participants enrolled with Protocol Amendment 9 and those treated up to the Week 16 timepoint under the original maintenance dosing regimen. Where available, individual ECLIA-based anti-CZP antibody data will be tabulated by study visit and Baseline age stratum (all study participants, 2 to 5 years, 6 to

11 years, and 12 to 17 years). In addition, safety and efficacy profiles by antibody titers (or titer categories) may be investigated.

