13.5 Planned efficacy and health outcomes analyses

Summary statistics will be presented for efficacy and health outcomes variables using the FAS.

All efficacy and health outcomes variables results will be presented overall and separately for the 2 CZP dose regimens (original CZP dose regimen, reduced CZP dose regimen).

The following efficacy variables are defined as secondary variables in this study:

- PedACR30, PedACR50, PedACR70, and PedACR90 response rates at Week 16 as compared to Baseline.

The following efficacy variables are defined as other variables:

- PedACR30, PedACR50, PedACR70, and PedACR90 response rates at every visit except Week 16 and Final Visit as compared to Baseline.

For PedACR30, PedACR50, PedACR70, and PedACR90, results will be presented overall and by Baseline weight strata, as well as by age (2 to 5 years, 6 to 11 years, and 12 to 17 years), by concomitant MTX use, and by anti-CZP antibody status.

- Change from Baseline in number of joints with active arthritis at every visit except Final Visit.
- Change from Baseline in number of joints with limitation of range of motion at every visit except Final Visit.
- Change from Baseline in Physician's Global Assessment of Disease Activity (VAS) at every visit except Final Visit.
- Change from Baseline in CHAQ at every visit except Final Visit.
- Change from Baseline in Parent's Assessment of Arthritis Pain (VAS) at every visit except Final Visit.
- Change from Baseline in Parent's Global Assessment of Overall Well-Being (VAS) at every visit except Final Visit.
- Ratio to Baseline in CRP at every visit except Final Visit.
- Change from Baseline in JADAS at every visit except Final Visit. The JADAS is a composite disease activity score including the Physician's Global Assessment of Disease Activity, the Parent's Global Assessment of Overall Well-Being, the active joint count, and CRP.
- Percentage of study participants with Clinically Inactive Disease (CID), as defined in Section 11.10, at every post-Baseline visit except Final Visit.

- Percentage of study participants with clinical remission on medication (CRM), as defined in Section 11.10, at every post-Baseline visit from Week 24 onwards except Final Visit.
- Time (in days) to CID.
- Time (in days) to CRM.
- Change from Baseline in DMS at every visit except Final Visit.

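### The main original-regimen Week 48 concentration summary groups by starting regimen, so it pools full-dose samples with samples from early starters already cut to half dose

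*Protocol*

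**What the plan says.** Section 13.2.1 assigns each participant to the original or the reduced regimen by the regimen on which treatment began. One dose is enough, and membership of the original group holds "regardless of any subsequent switch to the reduced CZP dose regimen". The reduced group has the mirror rule.

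That section opens by speaking of safety and efficacy, but Section 13.4 carries the same labels into PK. Concentrations measured by ECLIA are summarised "by study dose regimen (original CZP dose regimen or reduced CZP dose regimen) for each PK sampling visit" and plotted "separately for study participants who began treatment according to the original CZP dose regimen or the reduced CZP dose regimen". The same section fixes the primary status: "Certolizumab pegol plasma concentrations levels at Week 16 and Week 48 will be assessed as primary variables in this study". Section 13.5 applies the labels to efficacy: "All efficacy and health outcomes variables results will be presented overall and separately for the 2 CZP dose regimens".

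Section 7.2.1 records why the starting label and the dose received can differ: "With Protocol Amendment 4, the maintenance dose in the study was reduced by 50% for all weight groups". Section 5.4.2.2 adds that Amendment 5 lowered loading doses for new enrollees only, so those open to a mid-study cut were the people who had begun on the original dose.

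Two provisions limit the problem. Section 13.4 plans PK subgroup analyses for "study participants enrolled with Protocol Amendment 9 and those treated up to the Week 16 timepoint under the original maintenance dosing regimen". Section 13.3 splits adverse events by the dose period in which they arose, and repeats the 16-week adverse event summary without those cut before Week 16.

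**The concern.** A mean taken over samples at two dose levels describes neither regimen. The row labelled original would read low at Week 48 for the regimen that Amendment 9 reopened enrollment to study. Section 5.4.1 rests the paediatric programme on comparing exposure with adults with RA, so a reader would naturally take this row as the exposure on the original dose.

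The protocol treats the distinction as important for adverse events and, up to Week 16, for PK. Nothing separates the early starters by dose received at Week 48, and no efficacy table does so at any visit.

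**Working it through.** **Does the stated 50% cut reproduce?** Weekly maintenance dose from Table 7-1, reduced over original:

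- 10 to <20 kg: (50/4)/(50/2) = 12.5/25 = 0.50
- 20 to <40 kg: (50/2)/(100/2) = 25/50 = 0.50
- 40 kg and above: (100/2)/(200/2) = 50/100 = 0.50

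It does, in all three weight groups, as dose per unit time.

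**Who is in the original-regimen row?** Section 13.8 gives 78 early starters and 30 more after Amendment 9, so up to 78 + 30 = 108. Stored samples from the 78 enter the ECLIA tables where volume allows (Section 13.4).

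**Could early starters have been cut before Week 48?** First visit was in 1Q 2012 (Section 5.1.1). The analysis behind the cut dates from June 2013 (Section 5.4.2.2), and enrollment was suspended as of 17 July 2013 (Section 6.3). The date of Amendment 4 is not in the sections available. If it took effect near the suspension (an assumption), anyone who started after about 15 August 2012, which is 48 × 7 = 336 days earlier, reached Week 48 after the cut. The earliest starters could have reached it on the full dose. Section 13.3 itself allows for cuts before Week 16.

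**How far does mixing move the mean?** Let s be the share of the 78 on the reduced dose at Week 48, and v the share of their samples with enough volume. Neither is given, so both are assumed. The half-dose fraction of the row is

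f = s·78v / (78v + 30).

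Section 2 describes exposure as approximately linear in dose. If half the dose gives half the concentration, then relative to the full-dose value

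- geometric mean ratio = 0.5^f
- arithmetic mean ratio = 1 − 0.5f.

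| s | v = 1: f | geometric ratio | v = 0.5: f | geometric ratio |
|---|---|---|---|---|
| 0.10 | 0.072 | 0.95 | 0.057 | 0.96 |
| 0.25 | 0.181 | 0.88 | 0.141 | 0.91 |
| 0.50 | 0.361 | 0.78 | 0.283 | 0.82 |
| 0.75 | 0.542 | 0.69 | 0.424 | 0.74 |
| 1.00 | 0.722 | 0.61 | 0.565 | 0.68 |

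Example: s = 0.5 and v = 1 give f = 39/108 = 0.361 and 0.5^0.361 = 0.78. Over the grid the arithmetic ratio runs from 0.97 to 0.64. A dropout of 20% applied equally to both cohorts cancels from f.

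**Spread.** Mixing adds f(1 − f)(ln 2)² to the log variance. An assumed true geometric CV of 30% would show as about 34% to 48%.

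**Group size after regrouping by dose received** (v = 1, before dropout): the full-dose group at Week 48 holds 30 + 78(1 − s), which is 108, 69 or 30 at s = 0, 0.5 or 1.

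**The case against.** The case against is substantial, and most of it limits the point without removing it.

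- **A clean estimate is already planned.** The Amendment 9 subgroup starts on the original dose and is sampled at Week 48. The other subgroup gives an unmixed Week 16 summary. Both stand. What remains is the main Week 48 row, and the early starters who reached Week 48 on full dose, whom no planned table isolates.
- **The analysis is descriptive.** No test or decision rule is attached to the primary PK variable. That lowers the severity; the label would still mislead.
- **The table label could be read as the regimen at the visit.** The plots use the starting regimen explicitly, and the two names are those defined in Section 13.2.1, so the starting-regimen reading is the sound one.
- **Linearity is a simplification.** Section 2 states it for Cmax and AUC after single doses, while these are predose samples. In the lowest weight group the cut was made by doubling the interval. With a 14-day half-life and a simple bolus model (an assumption), the predose ratio is (0.25/0.75)/(0.5/0.5) = 1/3, so half may understate the effect there.

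A reader might also infer more than the documents support:

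- **That moving reduced-dose participants up contaminates the reduced group's PK.** It does not: Section 9 and Table 5-1 stop concentration sampling in everyone enrolled before Amendment 9.
- **That the bridge to adult data is broken.** This is not shown. The PopPK model in Section 13.4 is parameterised in clearance, volume and absorption, and nothing says it uses the table label or that this mean is the quantity compared with adults.
- **That antibody tables share the fault.** Section 13.4 tabulates those by visit and age stratum, not by regimen.
- **That Week 16 PedACR in the reduced group is affected.** Up-switching follows Amendment 9, and Section 13.7 indicates that earlier active participants had already passed Week 24. Only later efficacy tables are exposed.
- **That efficacy should simply be cut at the switch.** An up-switch is at the Investigator's discretion and may follow poor response, so such censoring may be informative. Grouping by starting regimen is a conventional choice for the main efficacy tables.

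**Conclusion.** The point holds for the main Week 48 concentration summary of the original regimen. The grouping rule is written into the protocol, and wherever any early starter had been cut by Week 48 the bias is downward. Its size is a scenario range: a geometric mean about 0.96 to 0.61 of the full-dose value, resting on dose-proportional exposure, on s between 10% and 100%, and on v between 50% and 100%. The lower end needs every early starter cut and every stored sample usable. The actual counts would settle it.

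For efficacy the point is narrower. Week 16 PedACR in the original group is mixed only by cuts made before Week 16, and later by-regimen tables can mix doses in both groups.

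This should be fixed, but it does not invalidate the study: the analyses are descriptive, and a smaller clean Week 48 estimate is already planned.

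**What to change.** **Section 13.4.** Tabulate Week 16 and Week 48 concentrations by the regimen in force when the sample was taken. Show samples drawn soon after a switch separately, with the window defined in advance. Keep the starting-regimen table as supportive, and report how many early starters had been cut by each timepoint and how many stored samples were usable.

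**Section 13.5.** Keep the starting-regimen tables as the main efficacy display. Add a supportive Week 16 PedACR table that leaves out original starters cut before Week 16, matching what Section 13.3 does for adverse events. In later by-regimen tables, identify switched participants, and state that cutting their data at a discretionary switch may be informative.

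**Cost.** Changed wording in the protocol and SAP, and a regimen-at-sample flag derived from dosing records already held. The downside is fewer samples per cell. No dose or clinical rule changes.

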13.2.2 Multicenter studies

Approximately 55 centers are planned to enroll the original 156 study participants into this study. A subset of these centers will be used to enroll the additional 30 study participants following Protocol Amendment 9. The enrollment per site is limited to a maximum of 12 study participants.

13.2.3 Coding dictionaries

Medications will be coded with the World Health Organization Drug Dictionary and AEs will be coded according to MedDRA[®]. In both cases, the version used will be that current to the Sponsor at the time of data capture.

13.3 Planned safety analyses

The incidence of serious TEAEs and TEAEs leading to permanent withdrawal of IMP will be assessed as primary safety variables in this study. Other safety variables include the incidence of TEAEs, TEAEs of interest, TEAEs by relatedness, TEAEs by severity, and TEAEs by duration of exposure. The primary summaries of safety will include all study participants in the SS, regardless of CZP dose. Safety variables will be summarized overall and separately for the 2 CZP dose regimens (original CZP dose regimen, reduced CZP dose regimen).

Safety summaries will include presentations of AEs, extent of exposure, laboratory values (hematology and biochemistry), vital signs, concomitant medications and procedures, and autoantibody (ANA and anti-dsDNA antibodies) concentrations. Urinalysis results will be listed. Tanner stages will be presented by category. Growth as measured by height and weight will be assessed in relation to a comparative population and this may include an assessment of any change after treatment with CZP.

For AEs, the exposure-adjusted incidence rate (EAIR) will also be calculated. For EAIR, the numerator will be the total number of study participants experiencing a particular AE. The denominator will be study participant-years, ie, the total summation of individual study participant-years at risk up to the first occurrence of the given AE for study participants with

that AE, plus the total study participant-years at risk for those study participants not experiencing that AE.

For the original CZP dose regimen subgroup, in addition to the overall presentation of AEs, AEs will be summarized separately for the periods of exposure to original CZP dose regimen and the reduced CZP dose regimen, in addition to exposure for study participants that switched from the reduced CZP dose regimen to the original CZP dose regimen following Protocol Amendment 9. Additionally, the frequency and percentage of AEs reported during the first 16 weeks of study medication exposure will be summarized separately for the 2 CZP dose regimens (original CZP dose regimen, reduced CZP dose regimen). This analysis will be repeated, excluding any study participants who switched from the original to the reduced CZP dose regimen prior to Week 16. Selected safety summaries will be presented overall and by Baseline weight strata, as well as by age (2 to 5 years, 6 to 11 years, and 12 to 17 years), by concomitant MTX use, and by anti-CZP antibody status.

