4.1.2 Safety variables

The primary safety variables will be the incidence of serious TEAEs and TEAEs leading to permanent withdrawal of IMP.

Adverse events will be solicited at every visit, recorded and coded according to Medical Dictionary for Regulatory Activities (MedDRA[®]) criteria.

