13.8 Determination of sample size

Based upon the ICH guideline for the assessment of safety, it is planned to enroll a sufficient number of study participants to this study to have a minimum of 100 with at least 12 months continuous exposure to CZP. Assuming a dropout rate of approximately 20%, it was originally determined that 125 study participants would need to be enrolled. At the time of Protocol Amendment 5, 78 study participants had been enrolled according to the original CZP dose regimen, and it was planned to enroll a further 78 study participants on the reduced CZP dose regimen, so that a comparable number of study participants on the reduced CZP dose regimens could be analyzed. Thus, the total number of study participants planned to be enrolled was increased to 156 study participants. Assuming a Screening failure rate of 25%, it is planned to screen 195 study participants in total.

With Protocol Amendment 9, an additional 30 study participants will be enrolled on the original dose regimen with the aim to enroll at least 5 study participants in each weight range of 10 to <20kg (22 to <44lb), 20 to <40kg (44 to <88lb), and ≥ 40 kg (≥ 88 lb).

Prior to the start of study conduct, simulations using the adult population PK model in pediatric study participants with JIA suggested that the planned sample size of 125 study participants was adequate for PK assessment purposes. Individual apparent clearance (CL/F) and volume of distribution (V/F) were simulated for a total of 125 study participants (using the same approach presented in C87079 report addendum 08 Oct 2008 performed for 190 study participants). In all age groups, the standard errors of both PK parameters, CL/F and V/F, relative to their mean were substantially <20%, with values ranging from 5.5 to 7.0% for CL/F and from 4.6 to 7.5% for V/F. A tabular summary of the results is presented below.

Table 13-1 PK simulation results for 125-study participant study sample size

| Parameter | Age group (years) | Mean | Standard error | Standard error/ Mean (%) |
|-----------|-------------------|-------|----------------|-----------------------------|
| CL/F | 4 to 8 | 0.253 | 0.015 | 6.0 |
| | 9 to 12 | 0.356 | 0.025 | 7.0 |
| | 13 to 17 | 0.432 | 0.024 | 5.5 |
| V/F | 4 to 8 | 2.90 | 0.134 | 4.6 |
| | 9 to 12 | 4.80 | 0.358 | 7.5 |
| | 13 to 17 | 6.80 | 0.334 | 4.9 |

CL/F=apparent clearance; PK=pharmacokinetic; V/F=apparent volume of distribution

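### The repeated 16-week adverse-event table excludes on a post-Baseline switch, which biases upward the original-regimen percentage with AEs leading to withdrawal in that one table

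*Protocol*

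**What the plan says.** Section 13.2.1 assigns participants to a regimen by how they began. The original-regimen subgroup is everyone who received at least one dose of that regimen, "regardless of any subsequent switch to the reduced CZP dose regimen".

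Section 13.3 then plans two versions of an early AE table. The first covers all starters: "Additionally, the frequency and percentage of AEs reported during the first 16 weeks of study medication exposure will be summarized separately" for the two regimens. The second is the same table with an exclusion: "This analysis will be repeated, excluding any study participants who switched from the original to the reduced CZP dose regimen prior to Week 16".

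On the cause of the switch, Section 7.2.1 states: "With Protocol Amendment 4, the maintenance dose in the study was reduced by 50% for all weight groups". On numbers, Section 13.8 says that at Amendment 5 "78 study participants had been enrolled according to the original CZP dose regimen", and that under Amendment 9 "an additional 30 study participants will be enrolled on the original dose regimen".

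Section 4.1.2 names the safety endpoints: "The primary safety variables will be the incidence of serious TEAEs and TEAEs leading to permanent withdrawal of IMP".

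**The concern.** The exclusion is defined by something that happens after Baseline and that only participants still being dosed can experience. Take two children who started on the same day, both due to have their dose reduced at Week 10. One stops for an AE at Week 7 and the other continues. The first never switches and stays in the repeated table. The second switches and is removed, with all AEs recorded before the switch.

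For AEs leading to permanent withdrawal the effect has a known direction. Nobody who switched can already have had such an event on the original dose, because the event would have ended dosing. The exclusion therefore takes people out of the denominator and takes no original-dose events of this type out of the numerator.

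Withdrawal-leading treatment-emergent AEs are one of the two primary safety variables. This is also the only 16-week regimen comparison that removes early switchers, so a reader may take it as the clean version. Amendment 9 added participants to support the safety assessment of the original regimen, and the table could make that regimen look somewhat worse through selection alone.

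**Working it through.** **Plan figures.** The protocol gives no figure for this table. Section 13.8's original enrolment target reproduces: 100/(1 − 0.20) = 125. The denominator of 78 agrees with the original-regimen Week 12 response rates in Sections 1 and 5.4.2: 59/78 = 75.6% and 50/78 = 64.1%.

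**Inputs**
- N = 78 + 30 = 108 original-regimen starters. The 30 enrolled under Amendment 9 do not face the Amendment 4 switch, but they belong to the subgroup.
- m = number due to switch before Week 16. Not stated; 10, 20 and 40 are assumed.
- p = true 16-week risk of an AE leading to withdrawal. Assumed 5%, with 8% as a variant.
- Switch time U, assumed uniform over Weeks 4 to 16 and unrelated to the participant's condition. Constant hazard λ.

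**Formula**
- λ = −ln(1 − p)/16. For p = 0.05, λ = 0.003206 per week.
- q = mean probability of withdrawing before the switch = 1 − [exp(−4λ) − exp(−16λ)]/(12λ). This is 0.0315 for p = 0.05 and 0.0506 for p = 0.08.
- Percentage under the rule = [(N − m)p + mq] / [(N − m) + mq].

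The mq early leavers are kept and all have the event, so the result is a weighted average of p and 100%. It exceeds p whenever mq > 0, and equals p when m = 0.

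**Results, N = 108**

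| m | Numerator (p = 5%) | Denominator (p = 5%) | Result, p = 5% | Result, p = 8% |
|---|---|---|---|---|
| 10 | 98 × 0.05 + 0.315 = 5.215 | 98.315 | 5.3% | 8.5% |
| 20 | 88 × 0.05 + 0.630 = 5.030 | 88.630 | 5.7% | 9.0% |
| 40 | 68 × 0.05 + 1.260 = 4.660 | 69.260 | 6.7% | 10.7% |

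Maintenance dosing starts at Week 6 (Table 7-1), so Weeks 6 to 16 is a reasonable variant. With p = 5%, q = 0.0346 and the results are 5.3%, 5.7% and 6.9%.

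**Check from the protocol's dropout rate.** Reading the 20% in Section 13.8 as dropout over 52 weeks, the 16-week risk of withdrawal for any reason is 1 − 0.8^(16/52) = 6.6%. With switch dates uniform over Weeks 0 to 16 and 10%, 30% or 50% of the 78 affected, the rule gives 6.9%, 7.5% or 8.4% among 108. If AEs leading to withdrawal are a constant share of withdrawals, they rise by the same ratios (1.04, 1.13, 1.26).

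**AEs not tied to stopping.** Assume a 50% risk over 16 weeks, with AE counting ended at withdrawal. The percentage moves from 48.5% to 48.4%, 48.2% or 48.0% in the same three cases. It falls slightly because the retained leavers have short follow-up.

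**Alternatives.** In simulation against a true 6.6% to 6.7%, censoring at the switch (Kaplan-Meier) and exclusion by start date regardless of withdrawal both returned 6.6% to 6.7%.

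**The case against.** The strongest reply is that little depends on this table. It is a descriptive repeat, shown beside its unexcluded version, with no test or decision attached. Section 13.3 bases the primary safety summaries on the whole Safety Set regardless of dose. It also plans exposure-adjusted incidence rates (EAIR) and, for the original-regimen subgroup, AE summaries split by period on each regimen, which keep the switchers' original-dose experience. Section 13.3 does not say that AEs leading to withdrawal will be shown in the 16-week table at all. All of this stands and limits the point to one table. It does not make the exclusion sound. The by-period summaries are not stated to be restricted to 16 weeks, so they do not replace the early comparison.

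A second reply is that perhaps nobody was affected. Section 6.3 records that enrolment was suspended as of 17 Jul 2013, and 16 weeks later is 6 Nov 2013. If first doses stopped at the suspension and the reduction took effect after that date, no one switched before Week 16. The available text does not give the effective date of Amendment 4, so this is possible but unconfirmed.

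Stronger readings are tempting and are not supported. A reader might infer that original-regimen event rates in general are inflated; the check shows that AEs unrelated to stopping do not rise. A reader might infer that the primary safety results are distorted, or that this is the only planned view of original-dose safety free of reduced-dose exposure; the other summaries in Section 13.3 contradict both. Using 78 alone as the denominator would also overstate the size, because Section 13.2.1 puts the 30 later participants in the same subgroup.

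**Conclusion.** The point holds for the repeated 16-week table only, and there only for AEs leading to withdrawal and AEs linked to stopping. The direction follows from the protocol's own definitions, given that the switch was applied protocol-wide and so did not depend on how the participant was doing. The size rests on an unstated number of early switchers. At a true 5% the excess is about 0.3, 0.7 or 1.7 percentage points for 10, 20 or 40 due to switch, which corresponds to about 0.3, 0.6 or 1.3 wrongly retained participants. It is zero if nobody switched early. Nothing in the documents supports 40 over the lower figures. This is a modest defect in a supporting table, worth correcting because the correction is cheap.

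**What to change.** In the repeated table, replace the exclusion by one of two rules.

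1. Censor at the first reduced dose. Count events and person-time on the original regimen up to the switch or Week 16, whichever comes first, and report the EAIR and a Kaplan-Meier 16-week risk.
2. If a simple percentage is preferred, exclude by a fact fixed at Baseline: a first dose less than 16 weeks before Amendment 4 took effect at the site, whether or not the participant later withdrew.

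Under the second rule, report how many were excluded and list their pre-switch AEs. If the dates show that nobody switched before Week 16, say so; the repeat is then unnecessary.

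The cost is one descriptive table reprogrammed, with no new data. The second rule also loses the few early leavers whom the planned rule would have kept.
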